Virtual Informed Consent: The informed consent document will be emailed to participants and co-participants at the time of scheduling (or earlier by request), to provide the recipient enough time to review the document. Prior to other study activities, a study team member will set up a phone call or video session to review the consent paperwork together. At this phone appointment, a study team member will explain each section of the informed consent document, pausing to answer questions or clarify misunderstandings. The study team member will also use the Consent Decision-Making Capacity Tool to ensure that the individual providing consent is able to fully understand the decision they are making prior to providing consent. After the informed consent document has been reviewed, eligible participants or LARs/DPOAs will review the STIM+ Disclosure Packet Request Form to determine whether they would like to receive a written copy of their results post-disclosure, and whether they'd like to receive them via US mail system or office pickup. After reviewing the forms, participants will be asked to provide electronic signatures on each form. These can be completed through two methods: (a) the patient can download, sign, scan, and email the form back to the study team member, who will additionally sign as witness and study representative, or (b) the Signnow platform will be used to provide electronic consent. SignNow is a secure platform offered through University of Michigan, which is HIPAA-compliant and approved by Health Information Technology Services (HITS). A copy of the forms, with all signatures, will be emailed to the participant/co-participant or made available through SignNow.

In-Person Consent: Participants completing in-person sessions will be encouraged to follow the above procedures to complete the consent paperwork via phone or Zoom prior to their in-person session, even if they choose to sign the consent in person. This will allow the study team to assess consent decisional capacity and walk through the consent form thoroughly before the participant comes into the lab (which may be more burdensome).

Additional Screening & Scheduling: Following receipt of the signed informed consent documents, both the participant and any co-participants will be asked to complete the GDS-15 and BAI via phone or video (these can be conducted on the same call used to complete the consent documentation). Any individuals who score above the clinical cutoffs (GDS \geq 9; BAI \geq 16) for these measures will be ineligible to take part in the study, per eligibility criteria noted above. Additionally, all co-participants must be cognitively intact based on screening or recent evaluation. Co-participants whose scores fall below the cutoff for impairment will be considered ineligible for study participation. Their respective participants will also be asked to delay scheduling of their virtual visit until they can identify another interested and eligible co-participant. Once this secondary screening of the subjects has been completed, the study team will schedule the Education session.

Education & Decision-Making Assessment Session: Participants (and co-participants, as applicable) will take part in a single 90-minute session via video conference (see Table 2).

1. Participants and co participants will complete a baseline assessment of their knowledge and understanding of AD biomarker testing procedures, results, risks, and benefits (Disclosure Decision-Making Assessment Tool; see below). Immediately following this assessment, participants will be shown an interactive educational presentation reviewing AD, DAT, available treatments, and the risks, benefits, and limitations of PET A β and tau disclosure in regard to assessing AD pathology and risk for DAT development.
2. Educational Module – The psychoeducation module will consist of a brief, instructor-led Power-point presentation. This didactic will cover the following topics: (a) definition of Alzheimer's disease and dementia due to Alzheimer's; (b) the role of amyloid and tau in Alzheimer's disease; (c) how amyloid and tau were measured in the parent study (i.e., PET imaging, what 'positivity' means in this context); (d) limitations of these measurements; (e) basic AD risk associated with amyloid and tau; (f) potential benefits of knowing one's biomarker status; (g) potential risks of knowing one's biomarker status. This module will include multiple opportunities for the participants and their loved

ones to ask questions. These materials were adapted from existing materials currently used in the Risk Evaluation and Education for Alzheimer's Disease (REVEAL) study, of which Co-I [name] is Co-PI, as well as Co-I [name]'s R03. Participants will also be provided with written materials summarizing this information. Materials will be written in lay language to accommodate all participants in the study.

3. Disclosure Preferences & Decision-Making Capacity Assessment – The educational module contains several 'checks for understanding' that parallel the questions on the **Disclosure Decision-Making Assessment Tool (DDMAT)** after each section to determine whether the participant fully demonstrates decision-making capacity for risk disclosure (Aim 2). Specifically, to demonstrate *understanding* of the decision, participants or their designated DPOA/LAR will be asked to describe, in their own words, the purpose and procedures involved in personal biomarker disclosure. To demonstrate *appreciation* of the decision, they will be asked to describe possible risks and benefits of personal biomarker disclosure. To evaluate *reasoning*, they will be asked to discuss their personal weighing of these risks and benefits, and alternatives to participation. Finally, they will be asked to *communicate*, either aloud or in writing, whether they would like to move forward with biomarker disclosure. Participants' responses will be recorded and subsequently transcribed for later evaluation of themes and foci. After each question, the clinician will evaluate the response for completion, ensuring it complies with necessary standards. If respondents provide an erroneous or incomplete response (e.g., acknowledging only one of several risks), the examiner will return to the section of the Education module reviewing the missed information, present it again, and then repeat the DDMAT question. If respondents are not able to provide a full, accurate response after such review, the question will be considered 'failed'. To address Aim 2, we will record not only who was able versus unable to demonstrate disclosure decision-making capacity, but also the specific element(s) of decisional capacity that were failed. Such information provides important information about how to better structure content so as to maximize comprehension in future efforts.

If the participant does not demonstrate disclosure decision-making capacity and does not have a co-participant or LAR/DPOA, the participant's involvement in the study will be complete after this session, and they will not be invited to take part in the Part II Disclosure portion.

If the participant has a LAR/DPOA co-participant, that individual must demonstrate decision-making capacity for the participant to receive risk disclosure and agree with this decision. Participant decision-making capacity will still be assessed. Regardless of whether the LAR/DPOA wants the participant to complete risk disclosure, the study team will not move forward with sharing the participant's risk information with either party unless assent is provided by the participant. If the participant or designated LAR/DPOA does not demonstrate full decision-making capacity, the study team will not move forward with risk disclosure, and the dyad's involvement in the study will be complete.

If the participant brings a co-participant who is not the designated LAR/DPOA, the participant may allow that individual to make the decision regarding PET disclosure for them. If this option is selected, the co-participant will undergo disclosure decision-making capacity assessment. Participant decision-making capacity will still be assessed. Regardless of whether the co-participant wants the participant to complete risk disclosure, the study team will not move forward with sharing the participant's risk information with either party unless assent is provided by the participant. If the participant or designated co-participant does not demonstrate full decision-making capacity, the study team will not move forward with risk disclosure, and the dyad's involvement in the study will be complete.

4. Baseline Outcome Measurement (for Part II): In order to gather baseline measurements of the constructs of interest for Part II of the study, all participants in Part I will complete the five outcome measures listed in Section 3.4.

Table 2. Proposed Components of Part I Education

1. Consent for Education (may be completed pre-session; separate)

2. Education Presentation (participant with co-participant)
3. Participant Decision-Making Capacity Assessment (separate)
4. Co-Participant or LAR/DPOA Decision-Making Capacity Assessment (separate)
5. Participant & Co-Participant Baseline Outcome Measurement (separate)
6. Post-Session study team review of responses to determine Disclosure eligibility

Both participants and their respective co-participants who complete the Education session will each be compensated with \$10 paid via check after the session.

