The ethical principles of patient autonomy and beneficence must be carefully weighed against non-maleficence and protection of the potentially vulnerable population of cognitively impaired older adults¹⁶. AD Biomarker disclosure can occur only if patients (or their designated signors) fully understand the information to be shared, and appreciate the risks and benefits of knowing this information. Preliminary data from Co-I [name]'s R03 demonstrate that participants request risk disclosure for a variety of perceived benefits; however, 88% endorse having 'no concerns' about risks of amyloid or tau disclosure (Figure 1). These data, while likely reflective of a strong desire for disclosure in the larger population, indicate a **second ethical dilemma**: whether to share information with symptomatic participants who may have impaired decision-making capacity to engage in amyloid/tau disclosure.

Figure 1. Participants' perceptions of primary benefits and risks of AD biomarker disclosure (data from Co-I [name]'s R03)

Finally, results of the prior literature suggest that disclosure of biomarker information related to AD is both safe and well-tolerated among cognitively healthy participants. Studies examining post-disclosure psychological reactions are very limited in individuals with mild cognitive impairment, and non-existent for individuals already diagnosed with DAT. Further, no prior study has examined the impact of symptomatic patients' biomarker information on care partners who are likely impacted by their partners' health information related to AD and who are also likely to have a pivotal role in their partners' health care and future care in the event of worsening cognitive impairment. Additionally, prior studies have exclusively considered the negative psychological effects of risk disclosure, rather than the full range of emotional reactions and the empowering results that may follow disclosure. Therefore, we address this **third ethical dilemma** by evaluating both positive (e.g., relief, happiness, satisfaction, empowerment) and negative (e.g., depression, anxiety, anger, distress) effects of biomarker disclosure on symptomatic participants and their co-participants (e.g., care partners).

SECTION 2.2: Objectives & Hypotheses of the study

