- (1) Demonstrated intact decisional capacity for amyloid and tau PET disclosure

Part II Disclosure Exclusion Criteria: No additional criteria

For the proposed study, we will offer all of the participants who have completed all parent study procedures up to and during this one-year supplement funding period (we estimate up to 100 individuals) the opportunity to enroll in the supplement-related procedures.

Co-Participants: Co-participants are required for all participants with a diagnosis of DAT, given the likelihood that participants may have impaired decision-making capacity and/or need additional support following disclosure. Co-participants are also strongly recommended, though not required, for participants with a diagnosis of MCI except in the event a participant with MCI demonstrates impaired decision-making capacity, thus requiring a co-participant. Co-participants are defined as (a) those who are currently serving as a

caregiver to the participant, or would hypothetically serve in this role should the need arise; (b) individuals who know the participant well, as demonstrated by a relationship lasting at least five years, and contact (any modality) at least once per week. Co-participants must also be age 18 years or older, English-speaking, cognitively healthy, and without current severe or untreated depression and/or anxiety.

Of note, if participants have a dedicated legally authorized representative (LAR) or durable power of attorney (DPOA) for medical and/or research decisions, this individual must serve as the co-participant in order for the participant to take part in the study. Documentation of this legal designation must be provided.

SECTION 3.2 Recruitment Strategy

Participants for Part I: Education will be recruited from parent studies via invitation only. The study team will review participants who completed the parent study, screen these cases for any interim changes that might impact eligibility of the participant (or co-participant, if there is one), and contact dyads to determine interest in engaging in STIM+ Education.

All participants who demonstrate decisional capacity for disclosure (or have a co-participant or LAR/DPOA who demonstrate decisional capacity for disclosure) will be invited to take part in Part II: Disclosure by study team invitation.

SECTION 3.3 Procedures

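### Read literally, both stop rules in 3.3.1 end disclosure when the participant fails the capacity assessment even though a capable surrogate passes and the participant assents, which contradicts the invitation rule in 3.2

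*Combined protocol and SAP*

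**What the plan says.** **Stop rules (3.3.1 item 3).** There are three capacity paragraphs.

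- The first ends involvement for a participant who "does not demonstrate disclosure decision-making capacity and does not have a co-participant or LAR/DPOA".
- The second covers a dyad with an LAR/DPOA. Of the LAR/DPOA it says "that individual must demonstrate decision-making capacity for the participant to receive risk disclosure and agree with this decision". The participant is assessed as well and must assent. It ends: "If the participant or designated LAR/DPOA does not demonstrate full decision-making capacity, the study team will not move forward with risk disclosure".
- The third covers a co-participant who is not the LAR/DPOA: "the participant may allow that individual to make the decision regarding PET disclosure for them". Participant assessment and assent again apply. It ends: "If the participant or designated co-participant does not demonstrate full decision-making capacity, the study team will not move forward with risk disclosure".

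Both closing sentences add that the dyad's involvement is then complete.

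**Invitation rule (3.2).** Participants who demonstrate capacity, "or have a co-participant or LAR/DPOA who demonstrate decisional capacity for disclosure) will be invited to take part in Part II".

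**Aims (2.2).** Aim 1 predicts equally high interest and completion whatever the diagnosis. Aim 2 predicts poorer capacity in DAT and says this is overcome by disclosing to the impaired participant's legally authorized representative or healthcare provider.

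**Text bearing on intent.** The background before 2.2 states: "AD Biomarker disclosure can occur only if patients (or their designated signors) fully understand the information to be shared". Section 3.1 recommends but does not require a co-participant in MCI, "except in the event a participant with MCI demonstrates impaired decision-making capacity, thus requiring a co-participant". Section 5.2 lets an LAR/DPOA, or a co-participant whom the participant allows, give consent while the participant assents.

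**The concern.** These sentences control entry to the intervention. The participant is assessed even when someone else decides, so staff can hold two results, participant failed and surrogate passed, together with a rule joined by 'or'. Applied literally, the surrogate's pass counts for nothing.

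Three analyses would then be affected.

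- **Aim 1.** Completion falls among those who fail capacity because the protocol stops them, not because they chose to stop. If failure is commoner in DAT, as Aim 2 predicts, this produces a difference by diagnosis in the outcome for which Aim 1 predicts none.
- **Aims 3 and 4.** The DAT groups in the diagnosis-by-biomarker analyses of 3.5.2 contain only participants with intact capacity and, for Aim 4, their co-participants.
- **Consistency.** If different staff apply different readings, two eligibility rules are mixed in one dataset.

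Aim 2 itself and the interest count in Aim 1 are measured before the gate and are unaffected.

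**Working it through.** **Step 1: set the rules side by side.** Assume that the participant assents and that the surrogate is the LAR/DPOA or a co-participant to whom the decision was delegated.

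| Participant | Surrogate | 3.2 | 3.3.1 as worded |
|---|---|---|---|
| pass | pass | invite | proceed |
| fail | pass | invite | stop |
| pass | fail | invite | stop |
| fail | fail | no invitation | stop |

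The second row is the conflict at issue, and it arises under both stop sentences. The third row is a smaller mismatch: 3.2 omits the requirement that a surrogate who decides must pass. For the LAR/DPOA sentence, the second row also contradicts Aim 2. Aim 2 does not mention an ordinary co-participant, so it does not bear on the other sentence. The first capacity paragraph and the delegation option conflict only by implication: under the literal rule, having a surrogate would never rescue a participant who fails.

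**Step 2: the ceiling on DAT completion.** The documents give no MCI/DAT split of the 100, no DDMAT failure rate and no delegation rate, so all inputs here are assumptions. Let f be the share of DAT participants who fail. Let r be the share of those who have a passing LAR/DPOA or a passing delegated co-participant, and who assent. Everyone allowed to proceed is taken to complete.

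- Literal wording: ceiling = 1 − f
- Decision-maker rule: ceiling = 1 − f(1 − r)

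With 50 DAT participants:

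| f | Literal: stopped (ceiling) | Decision-maker rule, r = 0.5 | Decision-maker rule, r = 1 |
|---|---|---|---|
| 0.2 | 10 (80%) | 5 (90%) | 0 (100%) |
| 0.4 | 20 (60%) | 10 (80%) | 0 (100%) |
| 0.6 | 30 (40%) | 15 (70%) | 0 (100%) |

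**Step 3: effect on a completion-by-diagnosis test.** Section 3.5.2 plans a chi-squared test for Aim 1. I take it as completion compared between diagnoses, uncorrected, at an assumed 5% level. Further assumptions are 50 per group, 10% failure in MCI and the same r in both groups. With x MCI and y DAT completers,

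X² = 100(x − y)² / [(x + y)(100 − x − y)], significant if above 3.84.

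As a check at expected counts, literal wording with f = 0.4 gives x = 45 and y = 30, so X² = 100 × 225 / (75 × 25) = 12.0. The probability of significance sums Bin(x; 50, p_MCI) × Bin(y; 50, p_DAT) over all significant pairs:

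| DAT failure | Literal: MCI v DAT completion | Probability | Decision-maker rule, r = 0.5 | Probability |
|---|---|---|---|---|
| 20% | 0.90 v 0.80 | 0.30 | 0.95 v 0.90 | 0.14 |
| 40% | 0.90 v 0.60 | 0.95 | 0.95 v 0.80 | 0.66 |
| 60% | 0.90 v 0.40 | about 1.00 | 0.95 v 0.70 | 0.95 |

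At r = 1 nobody is stopped, and the probability is 0.

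**The case against.** The best reply is that context settles the meaning. The background allows designated signors to stand in for patients. The DDMAT description in 3.3.1 treats the participant or the DPOA/LAR as alternative respondents. Section 3.1 requires a co-participant when an MCI participant shows impaired capacity, which would be pointless if impairment ended participation anyway. Section 5.2 sets out surrogate consent with participant assent, and 3.3.2 sends Part II consent through the same procedures as Part I. A separate assent condition would add little if the participant also needed full capacity. On this view 'participant or designated' means whichever of the two is deciding.

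As to intent, that is probably right. But Section 5.2 concerns capacity to consent, not the DDMAT, and nothing overrides the two stop sentences. Each follows a statement that the participant is still assessed. In the LAR/DPOA paragraph the decision-maker has already been named, so naming the participant again invites the literal reading. The trial design text in 2.3, the Part II criterion and the summary-table criteria fit either reading and do not resolve it.

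Two further points for the sponsor stand. First, no single probability from Step 3 should be quoted alone: 0.95 belongs to one scenario, and the literal-wording range is 0.30 to about 1.00. Second, a reader might infer that Aim 2's healthcare-provider route has no procedure at all. Section 3.3.2 item 3 does provide a signed release under which findings can be discussed with medical providers. It follows disclosure, so it does not serve a participant stopped at the capacity gate.

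**Conclusion.** The contradiction is real and lies in the current text: both stop sentences in 3.3.1 conflict with 3.2, and the LAR/DPOA sentence also conflicts with Aim 2. It should be fixed. The likely intended rule is sound; the sentences do not state it.

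The number of dyads affected cannot be derived from the documents. The figures in Steps 2 and 3 show only that the effect on Aim 1 could be modest or decisive, depending on DAT failure and on how many of those who fail have a qualifying surrogate. They rest on assumed group sizes, failure rates and full completion otherwise.

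Three stronger readings are not supported.

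- A reader might infer a risk of disclosure to people who cannot understand it. The literal wording errs the other way, towards withholding.
- A reader might infer that dyads have already been wrongly stopped. The documents do not show how staff apply the rule.
- A reader might infer that rewording removes the problem for Aim 1. It does not: a participant who fails, has a co-participant who is not an LAR/DPOA and does not delegate is still stopped, which is why the table shows a remaining effect at r = 0.5.

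**What to change.** 1. Reword both stop sentences in 3.3.1 item 3. Disclosure does not proceed if the decision-maker does not demonstrate full capacity, or if the participant does not assent. The decision-maker is the LAR/DPOA where one exists; otherwise it is the participant, or the co-participant to whom the participant has delegated the decision.
2. Align 3.2 and the Part II inclusion criterion in 3.1 with this rule. Using the same wording in 2.3 and the summary table would be sensible.
3. For Aim 1, report non-completion due to the capacity gate separately from non-completion by choice, using the pass/fail results that 3.3.1 already records.
4. In Aim 2, delete the healthcare-provider route or limit it to the post-disclosure release in 3.3.2.

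The cost is a protocol amendment with IRB approval (5.1) while the trial is recruiting. No additional participants, visits or assessments are needed. Because the rule would be clarified mid-study, the report should identify any dyads already stopped under the old wording.
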